#### 14.3.4 Statistical Analysis Plan

A041701 is a randomized Phase II/III study. The study will open with accrual open to two arms (one experimental arm and one control arm). The total Phase II sample size is

expected to be approximately 262 eligible patients (131 patients per arm). The total Phase III sample size is expected to be 670 (335 patients per arm). In the event that the Alliance Data Safety and Monitoring Board (DSMB) releases the requested Phase II data, the hypothesis-generating analyses described here will be performed based on Phase II accrual. Otherwise, this proposal is mainly based on Phase III accrual. Because this substudy is being newly incorporated in a protocol amendment post-study activation (54 patients accrued as of 11/22/2019), the current accrual rate suggests that approximately 600 evaluable Phase III patients may participate in this substudy.

We assume that 60% patients treated on A041701 will achieve a CR/CRi. Of those achieving CR/CRi, we expect to have end-of-induction marrow samples for MRD assessment on 90% of patients (n=324), and blood samples on 95% of patients (n=342).

We note that the Cox regression models below will be stratified by treatment arm as appropriate. Multivariable analyses will be evaluated as a complement to each univariate analysis. Multivariable analyses will include baseline covariates age, gender, performance status, cytogenetic risk, white blood cell count, platelet count, bone marrow blast percentage, and number of induction courses (1 vs 2).

*1. Primary integrated objective (To evaluate whether the presence of MRD will be a strong predictor of relapse-free survival (RFS) in patients achieving a CR/CRi following induction chemotherapy):*

We expect that approximately 25% of patients who achieve a CR/CRi will have detectable MRD by flow cytometry using the current methodology. Log-rank test will be used to assess associations between MRD and RFS. And RFS will be estimated by the Kaplan-Meier method.

In the calculations below, the RFS is assumed to follow an exponential distribution with a median of 11.5 months (null hypothesis). For the RFS outcome (assuming 59 months of accrual and an additional one year of follow-up per protocol), the marrow results (n=324) will have 80% power to detect an absolute difference in median RFS of 5 months between MRD- and MRD+ patients (HR = 0.7), 13 months for MRD- versus 8 months for MRD+ with a two-sided alpha of 0.05, and the blood (n=342) results will have 83% power for the same effect size and alpha level. C-statistics will be calculated to quantify the model's ability to predict outcomes. We will also fit multivariable Cox regression models with both end-of-induction MRD (present vs absent) plus the covariates listed above.

In the event that the Alliance Data Safety and Monitoring Board (DSMB) releases the requested Phase II data, the hypothesis-generating analyses described here will be performed based on Phase II accrual. Similarly, because this substudy is being newly incorporated in a protocol amendment post-study activation (54 patients accrued as of 11/22/2019), the current accrual rate suggests that approximately 200 evaluable Phase II patients may participate in this substudy.

For the RFS outcome (assuming additional 18 months of accrual and an additional one year of follow-up per protocol), the marrow results (n=108) will have 63% power, and the blood (n=114) results will have 65% power for a HR of 0.6 and two-sided alpha of 0.05. C-statistics will be calculated to quantify the model's ability to predict outcomes. We will also fit multivariable Cox regression models with both end-of-induction MRD (present vs absent) plus the covariates listed above.

*To analyze the association of MRD with overall survival (OS), time-to-relapse (TTR, defined as the time from randomization to relapse, with death without relapse censored at time of death), and relapse risk: OS and TTR will be estimated using the Kaplan-Meier*

method, and compared using log-rank tests. Risk of relapse (RR) will be summarized using cumulative incidence estimates. Cox regression analyses will be used to assess the association between the outcomes of interest and the covariates listed above.

*To compare whether evaluate whether MRD from the peripheral blood provides similar prognostic information compared to bone marrow:* We will fit multivariate marginal Cox regression models (Wei, Lin, Weissfeld 1989) including either blood and marrow MRD results with covariates for sample type (blood versus marrow), and a second model both blood and marrow MRD, and a third model with the interaction between the two covariates. We will calculate C-statistics for each of these models.

*To compare the presence of MRD at the end of induction versus end of consolidation time points to determine if either of these better predicts RFS:* We will fit multivariate marginal Cox regression models (Wei, Lin, Weissfeld 1989) including either MRD results at the end of induction or at the end of consolidation. We will calculate C-statistics for each of these models.

*To compare the rates of MRD by treatment arm:* Two-way table and chi-square tests will be used to compare the MRD rates by treatment arm.

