## 4.7 Stratification Factors, Grouping Factors, and Treatment Assignments

Stratification factors: age (60-69 vs. 70 and older), performance status (0-1 vs. 2-4), de novo vs. secondary/therapy related AML

Grouping factors: phase II vs. phase III

The randomization routine is found in [Section 13.0](#) (Statistical Considerations).

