## **13.0 STATISTICAL CONSIDERATIONS**

### **13.1 Study Design**

This is an open-label, randomized phase II/III study.

The primary objective of the Phase II study is to determine based on the event-free survival (EFS) whether the combination of uproleselan plus daunorubicin/cytarabine should be tested further against standard of care: daunorubicin/cytarabine in the phase III component of this trial.

The primary objective of the Phase III study is to compare the OS between uproleselan plus daunorubicin/cytarabine versus the control arm (daunorubicin/cytarabine). Patients accrued during the Phase II portion of the trial will be used in the Phase III analysis.

Randomization: Randomization will be stratified on the following stratification factors: age (60-69 vs. 70 and older), performance status (0-1 vs. 2-4), de novo vs. secondary/therapy related AML. Patients will be randomized to receive one of the two treatment regimens with equal allocation using a permuted block method to balance the stratification factors.

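### The adjusted MRD models omit AML type (de novo v secondary/therapy-related), the third stratification factor, so the adjusted MRD hazard ratio could partly reflect AML type

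*Combined protocol and SAP*

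**What the plan says.** Section 4.7 names three factors: "Stratification factors: age (60-69 vs. 70 and older), performance status (0-1 vs. 2-4), de novo vs. secondary/therapy related AML". Section 13.1 names the same three for the randomisation.

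Section 14.3.4, the analysis plan for the E-selectin and MRD substudy (A041701-LC1), states: "Multivariable analyses will include baseline covariates age, gender, performance status, cytogenetic risk, white blood cell count, platelet count, bone marrow blast percentage". The list ends with number of induction courses. AML type is not in it.

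The list is then reused. For relapse-free survival (RFS), on both the Phase III and the Phase II basis, the plan says: "We will also fit multivariable Cox regression models with both end-of-induction MRD (present vs absent) plus the covariates listed above". The Cox analyses of overall survival and time to relapse refer back to the same list. The only stratification of these models is by arm: "the Cox regression models below will be stratified by treatment arm as appropriate".

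The same section describes the multivariable models as complementary to the univariate analyses. The primary integrated objective, whether MRD predicts RFS among patients in CR/CRi, is assessed with a log-rank test and Kaplan-Meier estimates.

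**The concern.** Stratified randomisation balances AML type between the treatment arms. It does nothing for the comparison of MRD-positive with MRD-negative patients, because MRD is measured after induction and is not assigned. In that comparison, any protection against confounding has to come from the model.

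If MRD positivity is more frequent in secondary or therapy-related AML, and such patients also relapse or die sooner after remission, a model without AML type will credit part of that difference to MRD. Cytogenetic risk is in the model and may carry some of the same information. However, the stratification factor is defined as de novo against secondary/therapy-related disease, not by karyotype.

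At stake is how the adjusted MRD hazard ratio is read, and the C-statistics of the adjusted models. The efficacy comparison of the two arms is not at stake.

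**Working it through.** **1. The lists side by side.**

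| Stratification factor (4.7, 13.1) | In the 14.3.4 covariate list? |
|---|---|
| Age | Yes |
| Performance status | Yes |
| De novo v secondary/therapy-related AML | No |

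No other section adds AML type to the MRD models. More open wording about further factors does occur, but for other analyses: baseline associations (13.2.2), molecular markers (14.2.4) and E-selectin level (14.3.3). The 14.3.4 models comparing blood with marrow, and end of induction with end of consolidation, name no AML-type term. No reason for the omission is given.

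**2. The plan's own figures.** The sample chain reproduces:
- Phase III basis: 600 × 0.60 × 0.90 = 324 marrow and 600 × 0.60 × 0.95 = 342 blood samples.
- Phase II basis: 200 × 0.60 × 0.90 = 108 and 200 × 0.60 × 0.95 = 114.

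The stated 80% power for marrow reproduces if all 324 patients are counted as events: √(324 × 0.25 × 0.75) × |ln 0.7| − 1.96 = 7.794 × 0.357 − 1.96 = 0.82, which gives 79.4%. The present point does not depend on this power figure.

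**3. Possible size, AML type alone.** The documents give no MRD rate and no RFS by AML type, so these inputs are assumptions:
- Secondary AML share *s*: 35% to 50%. The older-adult cohort in Table 1 had 13 of 25, or 52%.
- MRD-positive: 30% to 40% in secondary and 15% to 20% in de novo AML, chosen to sit near the plan's overall 25%.
- RFS hazard ratio *h*, secondary v de novo: 1.3 to 1.8.
- No true MRD effect.

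Bayes' rule gives the secondary share among MRD-positive (p₊) and MRD-negative (p₋) patients. The apparent MRD hazard ratio is then approximately the ratio of average hazards:

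(p₊h + 1 − p₊) / (p₋h + 1 − p₋)

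- Low end (30% v 20%, h = 1.3, s = 50%): p₊ = 0.15/0.25 = 0.600 and p₋ = 0.35/0.75 = 0.467. The ratio is 1.180/1.140 = **1.035**.
- High end (40% v 15%, h = 1.8, s = 35%): p₊ = 0.14/0.2375 = 0.589 and p₋ = 0.21/0.7625 = 0.275. The ratio is 1.472/1.220 = **1.206**.

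Both are before adjustment for anything else.

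**4. Cross-check by simulation.** Cox models were fitted to 300,000 simulated patients per scenario. RFS was exponential, with a median of 11.5 months in the reference group. There were 25% MRD-positive and 50% secondary AML, with 59 months' accrual plus 12 months' follow-up. The assumed associations, to be read as those remaining after the other covariates, were an odds ratio of 1.5 to 3 for MRD positivity in secondary v de novo AML, and an RFS hazard ratio of 1.25 to 2.0.

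| True MRD HR | AML type omitted | AML type included |
|---|---|---|
| 1.00 | 1.02 to 1.19 | 0.99 to 1.00 |
| 1.43 (= 1/0.7) | 1.45 to 1.67 | 1.42 to 1.44 |

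With the odds ratio set to 1 (AML type unrelated to MRD) there is no upward bias: 1.00 when the true value is 1.00, and 1.39 to 1.42 when it is 1.43.

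**5. Against sampling error.** Amendment 04 ended accrual, so the Phase II basis (108 marrow samples) is the relevant one. Even if every patient has an event, the standard error of the log hazard ratio is 1/√(108 × 0.25 × 0.75) = 0.222. The 95% limits are then a factor of exp(1.96 × 0.222) ≈ 1.55 either side. The assumed bias lies inside that.

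**The case against.** The case for leaving the plan alone has several sound parts.

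- The log-rank test for the primary integrated objective is unadjusted, so a covariate added to a complementary model does not change it. The objective asks whether MRD predicts RFS, and a marker that partly reflects AML type still predicts. This stands. The point reaches only the adjusted models.
- Section 14.3.2 calls the objectives exploratory, and 14.3.4 calls the analyses on Phase II accrual hypothesis-generating. This stands and limits the weight.
- Matching model covariates to stratification factors is a principle for the randomised comparison, so a count of two out of three is not in itself an error. This also stands. The reason to add AML type is that MRD groups are not randomised.
- The plan says what the models will include, not that nothing else may enter. True, but as written AML type is not specified.

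A reader might also infer that the documents show AML type to be prognostic here. They do not:
- Sections 4.7 and 13.1 give no reason for the stratification factors.
- The CR/CRi rates in Table 2, 9 of 12 de novo and 8 of 13 secondary, show no clear difference (Fisher p = 0.67). They concern reaching remission, whereas the MRD analysis starts from patients already in remission.
- The 5.95-month median survival on 7+3 in the trial described in Section 1.1, set against the 12 months assumed in 13.1.2, compares a result with a planning value. That trial also enrolled de novo AML with MDS-related cytogenetics, so it cannot isolate AML type.

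**Conclusion.** The omission is real: AML type is absent from the covariate list, enters the MRD models in no other way, and no reason is given. Its consequence is possible, not shown. The adjusted MRD hazard ratio is inflated only if AML type is related to both MRD and outcome after adjustment for the listed covariates, and the documents are silent on that.

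The 1.04 to 1.21 range rests on assumed inputs and ignores the planned adjustment. Adjustment for cytogenetic risk would reduce it, and it is nil if AML type is unrelated to MRD given the other covariates. The stronger inferences, that the test of the primary MRD objective is compromised or that the treatment comparison is affected, are not supported. This is a minor, nearly free improvement to an exploratory analysis.

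**What to change.** Before the MRD data are analysed, add to the covariate list in Section 14.3.4: AML type (de novo v secondary/therapy-related, as stratified at randomisation). Alternatively, stratify the MRD Cox models by AML type together with treatment arm. Either way the change carries through to the RFS, overall survival and time-to-relapse models that refer back to the list.

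The value is needed to randomise a patient, so no new data are required. The cost is a short phrase in the plan and one degree of freedom in each model.

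### The powered log-rank test of MRD against RFS pools both arms without stratifying by arm, so an arm effect can mix modestly with the prognostic effect of MRD

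*Combined protocol and SAP*

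**What the plan says.** Section 14.3.4 sets a primary integrated objective for the MRD substudy: whether MRD after induction predicts RFS among patients in CR/CRi. The test is given in one sentence: "Log-rank test will be used to assess associations between MRD and RFS". The power statements follow under that objective. For OS and time to relapse, the Kaplan-Meier estimates are again "method, and compared using log-rank tests".

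Arm appears in three places:
- "We note that the Cox regression models below will be stratified by treatment arm as appropriate". The sentence covers Cox models only, and the qualifier leaves the choice open.
- The Cox models are secondary: "Multivariable analyses will be evaluated as a complement to each univariate analysis". For the RFS question the plan adds "We will also fit multivariable Cox regression models with both end-of-induction MRD (present vs absent) plus the covariates listed above". Treatment arm is not among those covariates, so it enters only through the qualified stratification.
- "Two-way table and chi-square tests will be used to compare the MRD rates by treatment arm". The plan therefore treats an arm difference in MRD as possible.

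The expected MRD-positive share is a single figure for both arms: "We expect that approximately 25% of patients who achieve a CR/CRi will have detectable MRD by flow cytometry using the current methodology".

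**The concern.** Arm is a possible common cause. The trial tests whether uproleselan prolongs event-free time, and the substudy asks whether it changes MRD. If it does both, and part of the RFS benefit does not run through MRD, then MRD-positive and MRD-negative patients differ in their mix of arms as well as in MRD.

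The bias can go either way. If uproleselan lowers MRD and lengthens RFS, MRD looks more prognostic than it is within an arm. If it adds MRD-positive remissions while lengthening RFS, a real MRD effect is partly hidden. The pooled p-value and the arm-stratified Cox hazard ratio would then answer different questions.

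**Working it through.** **1. The plan's own power figures.** The Phase III basis is 600 × 0.60 × 0.90 = 324 marrow samples; the Phase II basis is 200 × 0.60 × 0.90 = 108. RFS is exponential with median 11.5 months, so λ = ln 2 / 11.5 = 0.0603 per month. With uniform accrual A and follow-up F, expected events are D = n[1 − (e^(−λF) − e^(−λ(A+F)))/(λA)].

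- n = 324, A = 59, F = 12: D ≈ 281. Freedman's formula with a 3:1 split and HR 0.7 gives z = √(3 × 281) × 0.3/(1 + 3 × 0.7) − 1.96 = 0.85, or 80%. The plan states 80%.
- n = 108, HR 0.6: the stated 63% is obtained by Schoenfeld's formula if every patient has an event: √(108 × 0.25 × 0.75) × |ln 0.6| − 1.96 = 0.34, or 63%. With A = 18 and F = 12, D ≈ 76, and the same formula gives about 49%.

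The stratified powers near 51% below are therefore not a cost of stratifying. They reflect the expected event count.

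**2. Which size applies.** Amendment 04 (sections 13.1.1 to 13.3) ends Phase III accrual whatever Phase II shows. The 324-patient basis can no longer be reached, so 108 is the relevant size.

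**3. Assumptions.** The documents give no MRD rate by arm. I took an overall 25%, split 30/20, 35/15 or 20/30 (control/uproleselan). They give no arm effect on RFS either. I borrowed HR 0.64 (the EFS design effect, section 13.1.2) and 0.75 (the OS design effect, same section), acting wholly outside MRD. Numbers of remitters per arm were taken as equal.

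**4. Results at n = 108.** Simulation, 20,000 trials per row, 18 + 12 months, pooled median RFS 11.5 months, two-sided 5%:

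| MRD+ control/uproleselan | Arm HR | No MRD effect: rejection, unstratified / stratified | MRD HR 0.6: power, unstratified / stratified |
|---|---|---|---|
| 25/25 | 0.75 | – | 51.9% / 51.9% |
| 25/25 | 0.64 | – | 50.6% / 51.8% |
| 30/20 | 0.75 | 5.6% / 5.0% | 57.9% / 51.4% |
| 30/20 | 0.64 | 6.2% / 5.3% | 59.6% / 51.3% |
| 35/15 | 0.75 | 7.0% / 5.3% | – |
| 35/15 | 0.64 | 8.5% / 5.4% | – |
| 20/30 | 0.75 | – | 46.3% / 50.7% |
| 20/30 | 0.64 | – | 42.5% / 50.9% |

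A large-sample calculation that instead sets the median of control MRD-negative patients to 11.5 months agrees. Unstratified rejection is 5.2–5.5% at 30/20 and 5.9–7.1% at 35/15. Power at 30/20 is 58.3–59.1% unstratified and 51.3–52.5% stratified.

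**5. The hazard ratio.** In the large-sample calculation with no MRD effect within arm, the pooled MRD-negative to MRD-positive HR is 0.94–0.96 at 30/20 and 0.89–0.93 at 35/15. With a true 0.60, the pooled HR at 30/20 is 0.57–0.58; the stratified HR stays at 0.60.

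**6. When nothing is mixed, and what stratifying costs.** If the arm changes only MRD or only RFS, the null rejection rate stays at 5.0%. If MRD rates differ but the arm has no effect on RFS, stratifying lowers large-sample power from 55.0% to 54.4% (30/20) or 52.5% (35/15), so by at most about 2.5 points.

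**The case against.** The strongest reply has four parts.

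*An arm-stratified analysis of the same question is already planned.* This stands as mitigation: the Cox models address it, and the comparison of MRD rates by arm would reveal an imbalance. But the models are a complement to the log-rank test, and their stratification is discretionary.

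*The lack of stratification is read from silence.* Partly right. Section 13.2.1 calls the final OS test a log-rank test in one place and a stratified one in another, so silence is weak evidence. The sentence confining arm stratification to Cox models still favours the plain reading.

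*The assumed effects are generous.* This stands. The 0.64 belongs to EFS from randomization, which counts failure to reach CR/CRi as an event, whereas RFS here concerns patients already in remission. Any benefit that runs through MRD is mediation, not confounding.

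*The stakes are low.* This stands too. Section 14.3.2 lists the MRD work as exploratory, and section 14.3.4 describes the Phase II-based analyses as hypothesis-generating. No trial decision rests on this p-value.

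A reader might infer that the MRD result would be badly misleading. At n = 324 with 35/15 and arm HR 0.64, the pooled test rejects about 13–14% of the time under the null, and with the rates reversed (15/35) and an MRD HR of 0.7 its power is about 41% against 71% stratified. The documents do not support that as a description of this trial: that sample size is unreachable, and no document gives such MRD rates.

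**Conclusion.** The point holds as a modest, easily repaired weakness. The powered test, as written, does not separate MRD from treatment arm, although the plan allows that the arms may differ in both MRD and outcome. At 108 patients, false-positive inflation is slight for a 10-point MRD difference and small for 20 points. The more noticeable effect is on power: a 10-point difference shifts it by roughly 4 to 8 points in either direction, for reasons unrelated to the prognostic value of MRD.

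All of this rests on assumed MRD rates by arm and on an assumed arm effect on RFS that bypasses MRD. Without both effects there is no spurious association. It does not follow that the plan ignores treatment arm, or that any arm difference in MRD would invalidate the test.

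**What to change.** In section 14.3.4:
- State that the log-rank tests of MRD against RFS, OS and time to relapse are stratified by treatment arm.
- Remove the qualifier from the stratification sentence for the MRD Cox models, so that they are always stratified by arm. Section 14.3.3 already states this without a qualifier for the E-selectin Cox models.
- Report the arm-stratified Cox hazard ratio for MRD beside each test.

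Kaplan-Meier curves by MRD within arm are optional: 108 × 0.25 = 27 MRD-positive patients, or about 13 per arm, would give imprecise curves.

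The cost is a few words of SAP text and no new data. Power is essentially unchanged if MRD rates are equal across arms. At most about 2.5 points are lost if they differ, over the range examined, while arm has no effect on RFS.

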#### Phase II component

**Final analysis:** The Phase II decision-making will be conducted when at least 191 events are observed (approximately expected 37 months after the first patient enrolled). If less than 191 events are observed 2 years after Phase II accrual ends, then the Phase II decision will occur at the target data lock.

At the final analysis of the Phase II, it will be concluded that the experimental arm regimen is promising, if we a one-sided p-value  $< 0.10$  from the log-rank test favoring the experimental arm.

*As of Amendment 04, there will be no additional accrual to the Phase III component of the trial regardless of the outcome of the Phase II analysis. Given the maturity of follow-up on the current patients and no additional accrual to the trial, the final Phase III OS analysis will also be performed at the time of final Phase II EFS analysis. All Phase III alpha (one-sided 2.5%) will be spent at this analysis. The target data lock date is August 12, 2024.*

**Interim analysis:** We will conduct a futility interim analysis which will take place after 50% of the total events have occurred (approximately 25 months after the first patient enrolled). If at the planned interim analysis the hazard ratio is  $>1.0$  in favor of the control arm, the recommendation will be to stop further accrual to the experimental arm and conclude that the novel regimen does not have improved EFS.

We will suspend accrual between phase II and III. In order to protect the phase III comparison, the results of the phase II portion will only be released to the FDA and/or industry sponsors for regulatory purposes, contingent upon the approval and recommendation from the Alliance Data Monitoring Committee. Other than that, the Alliance DMC will only release whether the criteria for continuation to Phase III have been satisfied and not any of the actual results.

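### Section 14.3.4 pairs HR 0.7 with median RFS of 13 v 8 months, which give HR 0.615, and its Phase II powers of 63% and 65% are too high for the stated 18+12 months

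*Combined protocol and SAP*

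**What the plan says.** Section 14.3.4 (substudy A041701-LC1, primary integrated objective) compares RFS by log-rank test between MRD-negative and MRD-positive patients in CR/CRi. It expects that "approximately 25% of patients who achieve a CR/CRi will have detectable MRD by flow cytometry", and takes RFS to follow an "exponential distribution with a median of 11.5 months (null hypothesis").

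- **Phase III basis.** "assuming 59 months of accrual and an additional one year of follow-up per protocol", the marrow set (n=324) is given 80% power and the blood set (n=342) 83% at two-sided 0.05. The target is an absolute "difference in median RFS of 5 months between MRD- and MRD+ patients (HR = 0.7), 13 months for MRD- versus 8 months for MRD"-positive patients.
- **Phase II basis.** If the DSMB releases the data, "the hypothesis-generating analyses described here will be performed based on Phase II accrual". Here, "assuming additional 18 months of accrual and an additional one year of follow-up per protocol", the text states that "the marrow results (n=108) will have 63% power, and the blood (n=114) results will have 65% power for a HR of 0.6" at two-sided 0.05. It gives no medians for HR 0.6 and names no power method for either basis.

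Section 13.2.1 now says that "there will be no additional accrual to the Phase III component of the trial". Section 13.5 says that the EFS and OS data will be requested for release at the final Phase II EFS analysis.

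**The concern.** Under exponential RFS the hazard ratio is the inverse ratio of the medians. The sentence therefore gives one effect in two forms that cannot both be true, and a reader cannot tell which one the power belongs to. The choice moves the power by 15 to 21 points.

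The Phase II powers raise a separate question: whether 18+12 months yields enough events to support them. They now matter more than the Phase III figures, because accrual has ended and the Phase II set is what remains. A null MRD result would be read against a power that the stated inputs do not deliver.

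**Working it through.** **Inputs, all from Section 14.3.4.** Exponential RFS; 25% MRD-positive; two-sided 0.05; 59+12 months with HR 0.7 or 13 v 8 months; 18+12 months with HR 0.6. The sample sizes reproduce: 600 × 0.60 × 0.90 = 324 and 600 × 0.60 × 0.95 = 342; 200 × 0.60 × 0.90 = 108 and 200 × 0.60 × 0.95 = 114.

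**Assumptions not in the documents.** Uniform accrual, no dropout, and which group the 11.5-month median describes. For the last, MRD-negative medians of 11.5 to 13 months are used at HR 0.7, and 11.5 to 13.3 months at HR 0.6.

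**Step 1: the hazard ratio.**
- 8/13 = 0.615.
- The medians agree with the stated overall median: 0.75·2^(−m/13) + 0.25·2^(−m/8) = 0.5 gives m = 11.45 months, against 11.5 stated.
- HR 0.7 with an overall median of 11.5 gives 12.61 v 8.83 months, a difference of 3.8 months rather than 5.
- 8/11.5 = 0.696, so 0.7 may be MRD-positive against the null median. The text, however, labels it as MRD-negative against MRD-positive.

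**Step 2: formulas.** With accrual A, follow-up F and hazard λ = ln 2/median:
- P(event) = 1 − [e^(−λF) − e^(−λ(A+F))]/(λA)
- d = n[0.75·P(event, MRD−) + 0.25·P(event, MRD+)]
- Schoenfeld power = Φ(√(0.1875·d)·|ln HR| − 1.96)
- Freedman power = Φ(√(3d)·(1−HR)/(1+3·HR) − 1.96)

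A log-rank simulation (20,000 runs) was the third method.

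**Step 3: Phase III basis, A=59, F=12.** Example for n=324, 12.61 v 8.83 months: d = 280.0. Freedman: √840 × 0.3/3.1 = 2.805, and Φ(2.805 − 1.96) = 80.1%. Schoenfeld: √52.5 × 0.3567 = 2.584, and Φ(2.584 − 1.96) = 73.4%.

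| n (stated power) | Effect | Events | Schoenfeld | Simulation | Freedman |
|---|---|---|---|---|---|
| 324 (80%) | HR 0.7 | 278-286 | 73-74% | 75-76% | 80-81% |
| 324 (80%) | 13 v 8 | 279 | 94.0% | 95.1% | 97.5% |
| 342 (83%) | HR 0.7 | 293-302 | 75-77% | 77-78% | 82-83% |
| 342 (83%) | 13 v 8 | 295 | 95.1% | 95.8% | 98.0% |

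The stated 80% and 83% are reproduced at HR 0.7 by Freedman. No method gives them at 13 v 8 months.

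**Step 4: Phase II basis, A=18, F=12, HR 0.6.** Example for n=108, 13 v 7.8 months: d = 75.9. Freedman: √227.7 × 0.4/2.8 = 2.156, and Φ(2.156 − 1.96) = 57.8%.

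| n (stated power) | Events | Schoenfeld | Simulation | Freedman |
|---|---|---|---|---|
| 108 (63%) | 75-80 | 48-51% | 53-56% | 57-60% |
| 114 (65%) | 79-85 | 50-53% | 55-58% | 60-62% |

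Solving for events at HR 0.6, 63% power needs 85.8 (Freedman) or 107.4 (Schoenfeld), and 65% needs 89.8 or 112.4. The stated accrual and follow-up give at most about 80 and 85.

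**Step 5: where 63% and 65% could come from.** They appear only if a stated input changes. Counting every patient as an event gives 63.3% and 65.6% by Schoenfeld. Freedman with 30+12 months, using the whole Phase II accrual period in Section 13.3, gives about 61-64% and 64-66%. Neither matches the 18+12 months written, and neither source can be confirmed.

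**The case against.** The mismatch between 0.7 and 13 v 8 months is not in dispute. The case against concerns weight.

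- **The Phase III powers are right for HR 0.7 by Freedman**, so that defect is a mislabelled effect and not a miscalculated power. This stands; the 94-98% only shows what the other reading would imply.
- **The Phase II gap depends on the method.** By Freedman, the formula that fits the Phase III figures, it is about 2.5 to 6 points; the larger gaps come from other formulas. This also stands as to size, but Freedman is the most favourable of the three methods and still falls short.
- **Actual follow-up will be longer than 12 months.** Section 13.2.1 sets the target data lock at August 12, 2024. The end of Phase II accrual is not given, so this has to be assumed. At 18+24 months Freedman gives 66-68% (n=108) and 68-70% (n=114), and Schoenfeld 56-58% and 58-60%. At 18+36 months they give 69-71% and 72-73%, and 60-61% and 62-63%. The stated figures may therefore be close to, or below, the power finally available. That limits the practical harm, but it does not make 63% and 65% correct for the 18+12 months to which the text ties them.

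**Conclusion.** Both parts hold, as a minor point.

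The first is plain arithmetic: 13 v 8 months is HR 0.615, and the stated 80% and 83% belong to HR 0.7. It needs only the exponential model that the plan assumes.

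The second holds under all three methods checked. At 18+12 months the Phase II powers are overstated by about 2.5 to 6 points by Freedman, 7 to 10 by simulation and 12 to 15 by Schoenfeld. This rests on uniform accrual, no dropout and the range of medians used. Dropout would lower the power, and so would reading 11.5 months as the MRD-positive median (41-51% by Schoenfeld and Freedman).

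The substudy is hypothesis-generating. No sample size, boundary, or EFS or OS conclusion depends on these figures.

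**What to change.** In Section 14.3.4:

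1. State one effect: either 13 v 8 months with HR 0.615, or HR 0.7 with about 12.6 v 8.8 months.
2. Name the power method and give the expected events under the 25:75 split, with the accrual and dropout assumptions and the medians behind HR 0.6.
3. Restate the powers to match. For Phase II, preferably replace 18+12 months with the follow-up actually available at data lock and recompute. If 18+12 months is kept, state about 53-58% by log-rank simulation (48-62% across methods).

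The cost is a few restated figures and one sentence on method. No new samples, data or analyses are needed.
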